5.1.2 Protocol Deviations

A Per-Protocol analysis will not be carried out and therefore no Per-Protocol population is defined. However, protocol deviations which may have impact on method failure PI will be reviewed during DRM and will be classified as according to their impact.

Tables

No.	Name	Analysis set	Comments
Table 15.1.7.1.1	Deviations Leading to Pregnancies Exclusion from the Method Failure Analysis	Modified Full Analysis	Number and percentage of pregnancies which were excluded from method failure analysis will be presented. Percentage will be based on total number of subjects in MFAS. Data of centers 104 and 120 will be excluded.
Table 15.1.7.1.2	Deviations Leading to Cycles Exclusion from Analyses	Modified Full Analysis	Number and percentage of cycles which were excluded from some analysis will be presented. Percentage will be based on total number of cycles from subjects in MFAS. Data of centers 104 and 120 will be excluded.

Listings

No.	Name	Analysis set	Comments
Listing 16.2.1.4	Protocol Deviations Reported by Investigators	Enrolled	Protocol deviation from eCRF will be listed for the subjects from ES.

5.1.3 Inclusion/Exclusion

The trial specific inclusion/exclusion criteria are presented in the Sections 9.2 and 9.3 of the Clinical Trial Protocol. For each criterion, as appropriate, a response of “Yes/No” is to be obtained at Visit 1a (Screening) and at Visit 1b (Medication Dispensation).

Listings

No.	Name	Analysis set	Comments
Listing 16.2.1.5	Screening Failures	Enrolled	Subjects who discontinued the trial during the screening phase prior to enrolment to the treatment phase will be listed. Reasons associated with the discontinuation will be displayed.
Listing 16.2.1.6	Inclusion Criteria Not Met and Exclusion Criteria Met	Enrolled	Listing of inclusion criteria which were not met and exclusion criteria which were met will be presented per subject.

5.2 Demographic and Other Baseline Characteristics**5.2.1 Demographics**

Demographic data collected at Visit 1a will include the following:

- Date of birth
- Ethnicity (Hispanic or Latino, Not Hispanic or Latino)
- Race (American Indian or Alaska Native, Asian, Black or African American, Native Hawaiian or Other Pacific Islander, White, Other)
- Highest level of education completed (No high school diploma, high school diploma or equivalent, some college, college degree or higher)
- Years of education completed for subjects who have no high school diploma
- Sexual activity.

Age in years

Age in years will be calculated as the difference between the date of birth and the date of informed consent/assent using the following SAS function:

Age = FLOOR(YRDIF(< date of informed consent >, < date of birth >, 'ACT/ACT'))

Breastfeeding

With Protocol Final Version 4.0, 16 November 2015 exclusion criteria have been changed and breastfeeding women were allowed to enter the study. Information on whether the subject is breastfeeding will be collected in the eCRF only on Protocol Final Version 4.0, 16 November 2015.

Additional categories which will be presented in demographic and subgroup tables:

- Breastfeeding status, defined as
 - Breastfeeding
 - Non-breastfeeding

- Age categories (the 1st rule), defined as
 - ≤35 years (at study enrollment)
 - >35 years (at study enrollment)
- Age categories (the 2nd rule), defined as
 - 15-17 years (at study enrollment)
 - 18-35 years (at study enrollment)
 - >35 years (at study enrollment)
- Non-breastfeeding women and race, defined as:
 - Non-breastfeeding women, American Indian or Alaska Native
 - Non-breastfeeding women, Asian
 - Non-breastfeeding women, Black or African-American
 - Non-breastfeeding women, Native Hawaiian or Other Pacific Islander
 - Non-breastfeeding women, White
 - Non-breastfeeding women, Other
- Non-breastfeeding women and BMI, defined as:
 - Non-breastfeeding women, BMI < 30 kg/m²
 - Non-breastfeeding women, BMI ≥ 30 kg/m²
 - Non-breastfeeding women, 25 kg/m² < BMI < 30 kg/m²²
- Sexual activity status, defined as:
 - Active
 - Non-active

Baseline characteristics of the subjects include:

- Body height (cm) at screening visit
- Body weight (kg) at screening visit
- BMI (kg/m²) at screening visit
- Systolic blood pressure (mmHg) at screening visit
- Diastolic blood pressure (mmHg) at screening visit
- Pulse rate (bpm) at screening visit.

Median value from the 1st, 2nd and 3rd measurements for systolic, diastolic blood pressure and pulse rate will be summarized.

Tables

No.	Name	Analysis set	Comments
Table 15.1.8.1.1	Demographics	Safety	Default descriptive statistics for age (years) and years of education completed for subjects who have no high school diploma will be presented. Frequency tabulations for categories defined in Section 5.2.1 will be included. Percentage will be based on the number of subjects with non-missing data in the SS. Data of centers 104 and 120 will be excluded.
Table 15.1.8.1.2	Demographics	Modified Full Analysis	Default descriptive statistics for age (years) and years of education completed for subjects who have no high school diploma will be presented. Frequency tabulations for categories defined in Section 5.2.1 will be included. Percentage will be based on the number of subjects with non-missing data in the MFAS. Data of centers 104 and 120 will be excluded.

² 25 kg/m² < BMI < 30 kg/m² category is in addition to the protocol.

Table 15.1.9.1.1	Subgroups	Safety	Number and percentage of subjects included all subgroups from Section 3.2 will be provided. Percentage will be based on the number of subjects with non-missing data in the SS. Data of centers 104 and 120 will be excluded
Table 15.1.9.1.2	Subgroups	Modified Full Analysis	Number and percentage of subjects included all subgroups from Section 3.2 will be provided. Percentage will be based on the number of subjects with non-missing data in the MFAS. Data of centers 104 and 120 will be excluded.
Table 15.1.10.1.1	Baseline Characteristics at Screening	Safety	Body height, weight, BMI, systolic and diastolic blood pressure, pulse rate will be summarized for subjects in the SS. Data of centers 104 and 120 will be excluded.
Table 15.1.10.1.2	Baseline Characteristics at Screening	Modified Full Analysis	Body height, weight, BMI, systolic and diastolic blood pressure, pulse rate will be summarized for subjects in the MFAS. Data of centers 104 and 120 will be excluded.

Listings

No.	Name	Analysis set	Comments
Listing 16.2.1.7	Demographics	Enrolled	Demographics will be listed for the subjects in the ES.

5.2.2 Substance Use

Substance use for the subjects include:

- Smoking status at screening visit (Non-smoker, Current smoker, Ex-Smoker, Nicotine replacement therapy)
- Smoking start date
- Number of cigarettes per day
- Date of smoking cessation
- Alcohol status (Abstainer, Moderate drinker, Excessive drinker)

Smoking duration (years)

Smoking duration in years for current smokers will be calculated as the difference between the start date of smoking and the date of Visit 1a using the following SAS function:

INT(YRDIF(<smoking start date>,<Visit 1a date>,'ACT/ACT'))

Non-smoking duration (years)

Non-smoking duration in years for ex-smokers will be calculated as difference between smoking cessation date and the date of Visit 1a using the following SAS function:

INT(YRDIF(<date of smoking cessation>,<Visit 1a date>,'ACT/ACT'))

Imputation of missing/incomplete dates:

Incomplete dates will be imputed in the following way:

for incomplete/missing smoking start date:

- the first day of the month, if only day is missing
- 1st of January, if the year is available but the day and month are missing
- if date is completely missing smoking duration will be set to missing

for incomplete/missing smoking cessation date:

- the last day of the month if only the day is missing, unless the year and the month of smoking cessation and Visit 1a are the same then the day of Visit 1a will be imputed
- 31st of December if only the year is available unless Visit 1a was performed at the same year then the day of Visit 1a will be imputed
- for completely missing dates Visit 1a date will be imputed.

Pack years smoking history:

A pack year is a unit for measuring the amount a subject has smoked over a long period of time. It will be calculated as follows:

$$\text{Number of pack years} = \frac{\text{number of cigarettes per day}}{20 \text{ (1 pack has 20 cigarettes)}} \times \text{smoking duration (years)}$$

Tables

No.	Name	Analysis set	Comments
Table 15.1.11.1.1	Substance Use	Safety	Smoking duration, number of cigarettes per day, pack-years and non-smoking duration will be summarized as continuous data. Smoking status and alcohol status will be presented by means of default frequency tabulation. Percentage will be based on the number of subjects with non-missing data in the SS. Data of centers 104 and 120 will be excluded.

Listings

No.	Name	Analysis set	Comments
Listing 16.2.1.8	Substance Use	Enrolled	Information about subjects' smoking and alcohol use will be listed for the subjects in the ES.

5.2.3 Medical History

Medical history includes any previous relevant illnesses, conditions and hospitalization during the last 6 months (longer in case of gynecological relevance) or any relevant ongoing (concomitant) diseases at Visit 1a.

Medical history of the subjects includes:

- Diagnosis
- Start date
- Stop date
- Ongoing tick box
- Treatment used (yes, no)

Medical history conditions will be classified as follows:

Prior medical history conditions are conditions which ended prior to Visit 1a.

Current medical history conditions are conditions which are ongoing at Visit 1a, i.e. "Ongoing" was ticked in eCRF at screening visit or stop date is after Visit 1a. In case of partial missing stop dates, a disease will be considered as ongoing at Visit 1a, unless the partial date information clearly indicates that the disease stopped prior to Visit 1a.

Also, medical history will be classified as **current medical history condition** if its stop date is completely missing and "Ongoing" status is not ticked.

Tables

No.	Name	Analysis set	Comments
Table 15.1.12.1.1	Prior Medical History Conditions	Safety	Prior medical history conditions will be summarized by displaying counts and percentages of subjects having at least one prior medical history condition and will be presented by SOC and PT. Subjects with two or more occurrences of the same disease/condition (as qualified by its PTs) will be counted only once for the respective PT. Percentage will be based on the number of subjects in the SS. Data of centers 104 and 120 will be excluded.
Table 15.1.12.2.1	Current Medical History Conditions	Safety	Current medical history conditions will be summarized by displaying counts and percentages of subjects having at least one current medical history condition and will be presented by SOC and PT. Subjects with two or more occurrences of the same disease/condition (as qualified by its PTs) will be counted only once for the respective PT.

			Percentage will be based on the number of subjects in the SS. Data of centers 104 and 120 will be excluded.
--	--	--	---

Listings

No.	Name	Analysis set	Comments
Listing 16.2.1.9	Medical History	Enrolled	Medical history conditions will be listed for the subjects from ES.

5.2.4 Gynecological History and VTE Risk Factors

Gynecological history of the subjects includes:

- Subject's age at menarche (years)
- Had the subject any deliveries (yes, no)
- Date of delivery
- Subject is currently breastfeeding tick
- Had the subject any miscarriages (yes, no)
- Date of miscarriage
- Had the subject any abortions (yes, no)
- Date of abortion

Deliveries, miscarriages and abortions calcification

Deliveries, miscarriages and abortions will be classified as follows:

- No delivery/miscarriage/abortion
- 1 delivery/miscarriage/abortion
- 2 deliveries/miscarriages/abortions
- 3 and more deliveries/miscarriages/abortions

Number of VTE risk factors classification

In addition to gynecological history findings a check of individual VTE risk factors will be performed at screening visit:

- Family history of thromboembolic illness (yes, no)
- Evidence of predisposing conditions for a vascular or metabolic disease (yes, no)
- Current smoker older than 35 years or non-smoker over 40 years old (yes, no)
- Body weight so that $BMI > 30 \text{ kg/m}^2$ (yes, no)

Number of VTE risk factors per subject will be classified as follows:

- No risk factor
- 1 risk factor
- 2 risk factors
- 3 and more risk factors
- Missing

Missing category will be set if at least one of individual VTE risk factors will be missing.

Tables

No.	Name	Analysis set	Comments
Table 15.1.13.1.1	Gynecological History	Safety	Subject's age at menarche will be summarized as continuous data. Frequency tabulations for subject with any deliveries/miscarriages/abortions and subjects with "No", 1, 2 or 3 deliveries/miscarriages/abortions will be presented. Percentage will be based on the number of subjects with non-missing data in the SS. Data of centers 104 and 120 will be excluded.
Table 15.1.14.1.1	VTE Risk Factors	Safety	Frequency tabulations for subject with or without corresponding VTE risk factor and subjects with "No", 1, 2

			or 3 corresponding number of VTE risk factors will be presented. Percentage will be based on the number of subjects with non-missing data in the SS. Data of centers 104 and 120 will be excluded.
--	--	--	--

Listings

No.	Name	Analysis set	Comments
Listing 16.2.1.10	Gynecological History	Enrolled	Gynecological history will be listed for the subjects from ES.
Listing 16.2.1.11	VTE Risk Factors	Enrolled	VTE risk factors will be listed for the subjects from ES.

5.2.5 Menstrual History

Menstrual history of the subjects includes (depending on the subject category some questions are not applicable):

- Subject category (Naive User, Previous User (No hormonal contraceptives for three months or more), Previous user (no hormonal contraceptives for less than three months), Switcher) Subcategories ‘Prior users of progestin-only methods(s)’, ‘Prior user of combination hormonal contraception only’ will be included for “Previous User” categories. Subcategories ‘Prior users of progestin-only methods(s)’, ‘Prior user of combination hormonal contraception only’ will be reviewed by Medical Monitor.
- Date of the first day of last menstrual bleeding before Visit 1a
- Was menstrual bleeding during last 6 cycles before V1a regular (yes, no)
- Mean intensity of menstrual bleeding during the last 6 cycles before Visit 1a (Light, Moderate, Heavy)
- Occurrence of spotting during the last 6 cycles before Visit 1a (yes, no)
- Occurrence of any unscheduled bleeding during the last 6 cycles before Visit 1a (yes, no)
- Intensity of unscheduled bleeding during the last 6 cycles before Visit 1a (Light, Moderate, Heavy)
- Occurrence of more than one menstrual bleeding absent during the last 6 cycles before Visit 1a (yes, no)
- Occurrence of at least one complete menstrual cycle before Visit 1a (yes, no)

Time since last menstrual bleeding (days)

Time since the last menstrual bleeding will be calculated as follows:

$$\begin{aligned}
 & \text{Time since last menstrual bleeding (days)} \\
 & = \text{Date of Visit 1a} - \text{Date of the last day of last menstrual bleeding}
 \end{aligned}$$

Tables

No.	Name	Analysis set	Comments
Table 15.1.15.1.1	Menstrual History	Safety	Default summary statistics for time since last menstrual bleeding (days) will be summarized. Frequency tabulations for the rest of menstrual history variables will be presented. Percentage will be based on the number of subjects with non-missing data in the SS. Data of centers 104 and 120 will be excluded.

Listings

No.	Name	Analysis set	Comments
Listing 16.2.1.12	Menstrual History		Menstrual history will be listed for the subjects from SS.

5.3 Prior and Concomitant Medications, Contraceptive Devices

Medications in current use, relevant medications used within six months before consent/assent and newly started medications during the trial are to be documented including over-the-counter (OTC) medications and herbal remedies. In addition, changes of therapy (including changes of frequency) during the trial are to be documented in the eCRF.

The following information is collected:

- Drug unique number
- Medication (trade name)/Therapy/Device
- Indication (if medication is used as a contraceptive, a checkbox “Contraceptive (incl. device)” is checked)
- Dose per intake
- Units
- Frequency
- Route
- Start Date
- Stop Date/Ongoing (checkbox “Ongoing” is checked)

For subjects with at least 1 intake of IMP, medications and therapies are classified as ‘prior’ or ‘concomitant’ based on start/stop dates:

Prior medications

Prior medications are defined as medications which stopped before the first intake of IMP (Day 1 of Cycle 1).

Concomitant medications

Concomitant medications are defined as medications taken during the treatment period. This includes any medication when:

- the start date is on or after the first IMP intake and on or before the last IMP intake
or
- the start date is before the first IMP intake and the stop date is after or on the first IMP intake day
or
- the start date is before the first IMP intake and the tick box “Ongoing” is marked.

Where only partial dates are present, the month and/or year may be sufficient alone for classification of therapies but in cases where this is not possible it will be treated as concomitant.

The number and percentage of subjects with at least one medication within each ATC 2nd level subgroup and preferred drug name will be presented for the respective set. The ATC 2nd level subgroups and preferred drug name within ATC 2nd level subgroup will be ordered alphabetically.

Tables

No.	Name	Analysis set	Comments
Table 15.1.16.1.1	Prior Medications, Therapies and Contraception	Safety	The number and percentage of subjects taking prior medications will be presented by ATC 2nd level subgroup and preferred medication name for subjects in the SS. Data of centers 104 and 120 will be excluded.
Table 15.1.16.2.1	Concomitant Medications, Therapies and Contraception	Safety	The number and percentage of subjects taking concomitant medications will be presented by ATC 2nd level subgroup and preferred medication name for subjects in the SS. Data of centers 104 and 120 will be excluded.

Listings

No.	Name	Analysis set	Comments
Listing 16.2.1.13	Prior and Concomitant Medications, Therapies and Contraception	Enrolled	Prior and concomitant medications, therapies and contraception will be listed for the subjects from ES.

5.4 Exposure to IMP and Compliance

5.4.1 Exposure to IMP

Exposure data include:

- Date of the first IMP intake (subject's diary)
- Date of the last IMP intake
- Date of IMP dispensation
- Number of white tablets dispensed
- Number of green tablets dispensed
- Date of IMP collection
- Number of white tablets collected
- Number of green tablets collected
- Numbers of tablets taken (subject's diary)
- Date of IMP intake with time in hours and minutes (subject's diary)

Exposure data are derived from appropriate eCRF pages and diary. If the 1st regular IMP intake (variable PILDT in subject's diary) was not entered, but the first IMP intake (variable BPILDTC in subject's diary) was entered then the 1st regular IMP intake will be derived from BPILDTC by adding time "T00:00".

Derived variables:

Overall treatment duration will be calculated as follows:

Overall treatment duration

$$= \text{Date of the last IMP intake} - \text{Date of the first IMP intake} + 1.$$

Cumulative exposure will be categorized as:

- ≥ 28 days
- ≥ 84 days
- ≥ 168 days
- ≥ 252 days

Missing Entries of IMP Intake in Treatment Diary

Missing IMP intake entries will be classified as total number of missing entries and consecutive missing entries per respective cycle. Total and consecutive number of missing entries will be categorized as:

- Total missing entries over up to 13 cycles
 - 0-2 missing entries
 - 3-5 missing entries
 - 6-8 missing entries
 - 9 or more missing entries
- Total missing entries per separate cycle
 - 0 missing entries
 - 1 missing entries
 - 2 missing entries
 - 3 missing entries
 - 4 or more missing entries
- Active tablet free interval. Active tablet free interval is >48h tablet free interval during the second IMP intake till day 24 of each cycle or >144h interval between the last IMP intake and the first IMP intake in consecutive cycles. Tablet free interval calculation will not take into account cycle days 25-28.

Tables

No.	Name	Analysis set	Comments
Table 15.1.17.1.1	Exposure to Investigational Medicinal Product	Safety	Default summary statistics for the overall treatment duration in days will be presented. Default frequency tabulation for cumulative overall treatment duration will be displayed. Percentage will be based on the number of subjects in the SS. Data of centers 104 and 120 will be excluded.
Table 15.1.18.1.1	Number of Subjects with at Least One Missing Entry of IMP Intake in Treatment Diary by Treatment Cycle and Overall	Safety	Numbers and percentages of subjects having at least one missing IMP intake will be presented. Number of missing IMP intakes will be presented by treatment cycle and overall. Percentage will be based on the number of subjects in respective cycle. Data of centers 104 and 120 will be excluded.
Table 15.1.19.1.1	Number of Subjects with Gaps between Two Active Tablet Intakes of More Than 48/144 Hours by Treatment Cycle and Overall	Safety	Numbers and percentages of subjects having >48h (or 144h for the 1 st IMP intake) active tablet free interval. Number of >48h (or 144h for the 1 st IMP intake) active tablet free interval will be presented by treatment cycle and overall. Percentage will be based on the number of subjects in respective cycle. Data of centers 104 and 120 will be excluded.

Listings

No.	Name	Analysis set	Comments
Listing 16.2.1.14	Drug Accountability	Enrolled	Dispensation and collection of IMP will be listed for the subjects from ES.

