2.3 Overall Trial Design

This trial is a prospective, multicenter, open-label, non-controlled trial in female subjects, age 15 or above who present to the clinic seeking contraception, who are postmenarcheal and premenopausal. Breastfeeding women are allowed to participate in the trial.

At V1a (screening), informed consent/assent will be obtained and the screening procedures will be performed. At V1b, after the results of the laboratory tests have confirmed the subject's eligibility, the subject will be provided with the investigational medicinal product (IMP) and an electronic diary and the subject will be instructed in their use. On anticipated start date of Cycle 1+2 days, the trial staff will call the subject for the confirmation of IMP start date. Afterwards, the subjects will attend Visits 2 to 5 at Day 20±2 of the 1st, 3rd, 6th and 9th cycle and Visit 6 at Day 29±2 of the 13th cycle. The follow-up (Visit 7) will take place 10-14 days after Visit 6. Once a month, on Day 10 (+ 2 days) of each cycle, the subjects will be contacted by the site staff to collect information on any adverse events which might have occurred.

The trial will include women who have never used hormonal contraceptives before consent/assent (naïve users), women who have not used hormonal contraceptives in the past three months before consent/assent or who have used hormonal contraceptives in the past but have a contraceptive-free time of less than three months before consent/assent (previous users) as well as women directly switching from another hormonal method (switchers). Women who have used hormonal contraceptives in the past but have a contraceptive-free time of less than three months before consent/assent are allowed to be included into the trial if they had at least one complete menstrual cycle before enrollment.

For naïve users and previous users, the first IMP intake will be on the first day of the next menstrual bleeding after Visit V1b. (If the menstrual bleeding starts in the evening, and the subject prefers to take her pill in the morning, then she may begin the first IMP intake the next day [Day 2 of the menstrual bleeding]). For a switcher, the first IMP intake will be on the day following the last active pill of the previous hormonal contraceptive. The subject is free to choose an intake time in the morning or evening

that suits her requirements. Breastfeeding women can start the first IMP any day starting six weeks after delivery.

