Method failure pregnancy*	All on-drug pregnancies of women who used the IMP correctly. Pregnancies are to be excluded from the calculation if in medication cycles of conception or in the previous medication cycles depending on the date of conception: 
 - not all active tablets are taken (based on returned medication, recordings in the e-diary and non-compliance based on DRSP levels, if necessary) - there is an active tablet free interval between the previous medication cycle and the medication cycle of conception. Tablet free interval will be determined by record from treatment diary. - vomiting or diarrhea is documented - administration of prohibited prior or concomitant therapy as detailed in Section 10.7 of the Clinical Trial Protocol is documented
Exposure cycles	28-day cycles, where at least one treatment diary entry of IMP intake is available. In addition, a cycle will be an exposure cycle if the subject become pregnant during this cycle regardless this cycle was a 28-day cycle or not.
Evaluable cycle	Cycles are exposure cycles with intercourse without back-up contraceptive at least once per cycle based on electronic diary question 'Did you have sexual

	
intercourse since the beginning of the cycle?" and answered with: 'Yes I had sexual intercourse without additional contraception'.
 
Also, cycle is to be defined as evaluable if:
 
 - Subject became pregnant at the respective cycle regardless back-up contraception was used or not. - Cycle has missing answer about intercourse or answered "I had NO sexual intercourse at all" but subject became pregnant at the respective cycle. 
Cycle will not be defined as evaluable if subject did not become pregnant and:
 
 - The question was answered with 'Yes I had sexual intercourse with additional contraception'. - Cycles with NO intercourse. - Cycle has missing answer about intercourse.
Perfect cycle*	
Evaluable cycles which have no:
 
 - >48h tablet free interval during the second IMP intake till day 24 of each cycle or >144h interval between the last IMP intake and the first IMP intake in consecutive cycles. Tablet free interval calculation will not take into account cycle days 25-28. - 4 or more days with forgotten tablets intake during 1-24 cycle days. - Protocol deviations having effect on this cycle.

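### A missing first-intake entry is timed at 00:00, which overstates the gap to the second tablet and can wrongly make Cycle 1 non-perfect when the next recorded intake is on Day 3

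*SAP*

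**What the plan says.** SAP Section 5.4.1 lists the diary data on tablet intake, which include the date and the time to the minute. It then gives a substitution rule. The trigger is "If the 1st regular IMP intake (variable PILDT in subject's diary) was not entered" while BPILDTC was entered; "then the 1st regular IMP intake will be derived from BPILDTC by adding time" T00:00. The whole regular entry has to be missing, not just its clock time.

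Two limits in hours are applied to intake times. Under Section 5.5 a perfect cycle has no ">48h tablet free interval during the second IMP intake till day 24 of each cycle" and no ">144h interval between the last IMP intake and the first IMP intake in consecutive cycles". Section 5.4.1 defines the active tablet free interval in the same terms. Table 15.1.19.1.1 reports "Numbers and percentages of subjects having >48h (or 144h for the 1 st IMP intake) active tablet free interval".

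On when tablets are taken, Section 2.3 says "The subject is free to choose an intake time in the morning or evening" that suits her.

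**The concern.** Midnight is not a likely intake time for women who choose between morning and evening. Stamping it on the first tablet moves that tablet earlier than it was and lengthens the interval to the second. The shift equals the true clock time, so it is larger for evening takers than for morning takers and has nothing to do with adherence.

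Gap status helps decide whether a cycle is perfect. Perfect cycles are the denominator of the method-failure PI, feed the method-failure life tables, and limit which pregnancies count as method failures. A false gap would remove a cycle that is within the plan's own tolerance and report it as a dosing gap in Table 15.1.19.1.1.

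**Working it through.** The plan gives no figure to reproduce here, so the check is clock arithmetic.

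**Inputs**
- One tablet per day, so the planned interval is 24 h (SAP Section 2.5).
- Within-cycle limit >48 h and between-cycle limit >144 h (Sections 5.4.1 and 5.5).
- Imputed first intake at 00:00 on Day 1 (Section 5.4.1).
- t1 = true clock time of the first tablet in hours; the second recorded intake is on Day d at clock time t2.

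**Formulas**
- True gap = 24(d − 1) + t2 − t1
- Computed gap = 24(d − 1) + t2
- Overstatement = t1, at most 23 h 59 min

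**Cases**

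| First tablet | Second recorded intake | True gap | Computed gap | Flagged: true / computed |
|---|---|---|---|---|
| 20:00 | Day 2, 20:00 | 24 h | 44 h | no / no |
| 08:00 | Day 2, 20:00 | 36 h | 44 h | no / no |
| 22:00 | Day 3, 01:00 | 27 h | 49 h | no / **yes** |
| 20:00 | Day 3, 08:00 | 36 h | 56 h | no / **yes** |
| 08:00 | Day 3, 07:00 | 47 h | 55 h | no / **yes** |
| 08:00 | Day 3, 09:00 | 49 h | 57 h | yes / yes |

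**General result**
- Day 2: the computed gap is at most 24 h + 23 h 59 min = 47 h 59 min, so it is never flagged.
- Day 3: the computed gap exceeds 48 h for every t2 after midnight, but the true gap exceeds 48 h only if t2 > t1. Over all 1,440 × 1,440 minute pairs, the computed gap flags 1,439/1,440 = 99.9% and the true gap 1,439/2,880 = 50.0%. These are shares of clock-time pairs, not of women.
- Day 4 or later: the true gap is at least 48 h 1 min (23:59 on Day 1 to 00:00 on Day 4), so both flag.

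A false flag therefore needs the second tablet to be more than 24 − t1 hours late and at most 24 h late. That is more than 4 h for a 20:00 taker and more than 16 h for an 08:00 taker.

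**Is this gap tested at all?** Read literally, the 48 h window opens at the second intake, and the gap before it is not examined. Three points favor testing.
- Table 15.1.19.1.1 attaches 144 h to the first intake and 48 h to the others, so a gap appears to belong to the intake that ends it.
- Both limits equal the planned interval plus 24 h: 24 + 24 = 48, and from Day 24 to Day 29, 5 × 24 + 24 = 144. That fits a rule meant for every pair of successive active tablets.
- Otherwise the gap falls under neither limit. A second intake on Day 4 would pass both intake criteria, since the forgotten-tablet criterion needs four or more days.

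**Size.** The frequency is not in the documents. Assume that 1% to 10% of the 920 planned women aged 35 or under have the missing entry (9.2 to 92), that all of them lose Cycle 1, that no pregnancy is lost, and that there would be C = 3,500 to 5,000 perfect cycles. The method-failure PI is then multiplied by C/(C − k), where k is the number of lost cycles:
- smallest: 5,000/(5,000 − 9.2) = 1.002
- largest: 3,500/(3,500 − 92) = 1.027

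**The case against.** The strongest objection is that two unusual events must coincide: the first regular entry is absent, and the second recorded intake falls on Day 3 no later than the clock time of the first. That stands, and it makes the bound above generous. The reading of the 48 h window is also unsettled. If the gap is not tested, the stamp has no effect on perfect-cycle status in Cycle 1. The table makes testing more likely than not, but only the sponsor can settle it.

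There is a partial safeguard. Listing DRM06 brings gaps over 48 h to the data review meeting, where a team including a physician judges the effect on perfect cycles (Section 3.3). The SAP does not say that gaps created by an imputed time will be identified or overridden.

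Four stronger readings are tempting and are not supported:
- *Evening takers who take their tablets on time lose Cycle 1.* They do not; no Day 2 intake is ever flagged.
- *The primary PI is affected.* It uses evaluable cycles, which have no gap criterion (Sections 5.5 and 5.5.1).
- *The same rule hides real gaps between blisters.* If BPILDTC were recorded per blister, the >144 h gap would be understated: 20:00 on Day 24 to 21:00 six days later is 145 h but would compute as 6 × 24 − 20 = 124 h. The documents do not say that it is. Sections 4.5 and 4.6 use first IMP intake for trial Day 1, although Table 15.1.19.1.1 uses it per cycle.
- *The error flatters the product.* Losing pregnancy-free cycles raises the method-failure PI. Only the loss of a cycle with a pregnancy would lower it, and pregnancies with an untaken active tablet are already excluded by the method-failure definition.

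**Conclusion.** The point holds in limited form. The 00:00 stamp gives wrong gap lengths, and if the first-to-second gap is tested against 48 h it produces false flags for second intakes on Day 3 at or before the clock time of the first. Evening takers reach that condition with less delay than morning takers.

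The reach is at most one Cycle 1 interval per woman concerned if BPILDTC is a single trial-level date. It touches only the secondary method-failure PI and life tables and Table 15.1.19.1.1. Under the assumed ranges the method-failure PI would rise by no more than about 3%, and probably less because the Day 3 condition is also needed. The number of women, the perfect-cycle count and the absence of pregnancies in lost cycles are assumptions. This is a minor correction, worth making because it is nearly free.

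**What to change.** Make three changes in SAP Sections 5.4.1 and 5.5:

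1. When PILDT is missing and BPILDTC is present, keep the BPILDTC date but replace T00:00 with the woman's own median recorded diary intake time, from the nearest cycle with recorded times.
2. If she has no recorded times, do not class that single interval as >48 h unless it exceeds 48 h whatever the clock time of the first tablet, that is, unless the second intake is on Day 4 or later. A rule that simply failed any interval with no tablet on Day 2 would reproduce the midnight stamp.
3. State that the first-to-second gap is tested against 48 h.

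It would also help to state whether BPILDTC is one date per woman or one per blister.

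The cost is a few lines of text and a small programming change, with no new data. The median leaves an error of a few hours for a woman whose first-day time was unusual. The fallback can leave a true Day 3 gap of up to 71 h 59 min unflagged (00:00 on Day 1 to 23:59 on Day 3), but only for women with no recorded times, which should be rare because intakes are recorded to the minute.
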